Investigators should be aware that special considerations are required for volume increases in patients with 2 infusion sites receiving a total dose (volume) of more than 50 mL. To ensure that volume increases do not exceed 25 mL/site, the infusions must be split between the 2 syringes, such that each infusion site will receive a different total volume. For example, if a patient is receiving a total dose of 60 mL divided equally between 2 infusion sites (eg, 30 mL/site), the first syringe could be increased to an infusion volume of 50 mL (an increase of 20 mL) and the

Name of Sponsor/Company: Octapharma USA, [name]	
Name of Investigational Product: CUTAQUIG	Protocol Identification Code: SCGAM-06
Name of Active Ingredient: Human Normal Immunoglobulin	Date of Final Protocol: 28-Aug-2019

second syringe would have an infusion volume of 10 mL. If this is tolerated, the next infusion volume increase could be 60 mL at 1 infusion site (an increase of 10 mL) and remain below the maximum allowed volume increase of 25 mL/site.

Cohort 2 (increased infusion rate - patients will receive CUTAQUIG weekly and increase infusion rates every 4 weeks): Patients will return to the clinic for the Treatment Period Baseline Visit, at which they will receive the same body-weight dependent (mg/kg) dose of CUTAQUIG but the infusion rate per site will be increased up to a maximum allowed flow rate increase per infusion site of 25 mL/hr/site for patients ≥ 40 kg or 10 mL/hr/site for patients < 40 kg. Patients will receive this new flow rate for 4 weekly infusions (Treatment Period Baseline and Weeks 1, 2, and 3), and return to the clinic at Week 4 for their next infusion at an increased infusion rate. This cycle will continue, with maximum allowed flow rate increases per infusion site of up to 25 mL/hr/site for patients ≥ 40 kg or up 10 mL/hr/site for patients < 40 kg every 4th infusion until reaching either: 1) a maximum flow rate (100 mL/hr/site) or the maximum flow rate achievable by the pump, or 2) the maximum tolerated flow rate (maximum flow rate based on Investigator's decision of patient's tolerance) – whichever is reached first.

Note: Clinical sites are encouraged to enroll patients that are either currently infusing with 24-gauge needle sets or willing to switch to 24-gauge needle sets. Patients using 27-gauge needles will not be able to achieve adequate infusion rates for this cohort as the needle gauge will not allow for this.

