3.3.2 Dosing

Stabilization Period: CUTAQUIG will be administered subcutaneously every week (± 2 days).

Treatment Period: CUTAQUIG will be administered subcutaneously every week (± 2 days) (or every other week [± 2 days], if applicable) for Cohort 1 (increased infusion volume) and Cohort 2 (increased infusion rate). For Cohort 3, CUTAQUIG will be administered every other week (± 2 days) at double the weekly dose.

Cohort 1 (increased volume at each infusion site – patients will receive CUTAQUIG weekly and increase infusion volumes every 4 weeks): Patients will return to the clinic for the Treatment Period Baseline Visit, at which they will receive the same body-weight dependent (mg/kg) dose but the volume will be increased by up to the maximum allowed volume increase per infusion site of 25 mL/site for patients ≥ 40 kg or 10 mL/site for patients < 40 kg. This volume increase per infusion site can be achieved by reducing the total number of injection sites while keeping the same or lower flow rates as received with their prior treatment. When introducing increased volumes to an infusion site, Investigators must attempt to maintain flow rates similar to or lower than prior infusions. This may require adjusting pump rate, tubing size, needle gauge, etc. Patients will receive this new volume per site for 4 weekly infusions (Treatment Period Baseline and Weeks 1, 2, and 3), and return to the clinic at Week 4 for their next infusion at an increased volume at each infusion site. This cycle will continue, with infusion volumes increasing by up to a maximum allowed volume increase per infusion site of 25 mL/site for patients ≥ 40 kg or 10 mL/site for patients < 40 kg every 4th infusion until reaching a patient's maximum dose (in mL), maximum tolerated volume (maximum volume based on Investigator's decision of patient's tolerance), or 100 mL.

at 1 injection site – whichever is reached first. For patients with maximum volume that exceeds 100 mL at 1 injection site, 2 injection sites should be used.

The following change in volume increments should be followed:

- Baseline: Reduce the number of injection sites by 1 (eg, patients using a 4 needle set will reduce to a 3 needle set). Tubing set, needle gauge, and pump rates (if applicable) may be adjusted to minimize flow rate variations. Investigators must ensure minimal flow rate changes at each injection site when increasing volume. Continue with the same infusion parameters at Weeks 1, 2, and 3.

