- Week 4: If the volume increase administered at Baseline through Week 3 is tolerated, reduce the number of injections sites again by 1 (eg, patients using a 3 needle set will reduce to a 2 needle set). Tubing set, needle gauge, and pump rates (if applicable) may be adjusted to minimize flow rate variations. Investigators must ensure minimal flow rate changes at each injection site when increasing volume. Continue with the same infusion parameters at Weeks 5, 6, and 7.
- Week 8: If the volume increase administered at Week 4 through Week 7 is tolerated, reduce the number of injection sites again by 1 (eg, patients using a 2 needle set will reduce to a 1 needle set). Tubing set, needle gauge, and pump rates (if applicable) may be adjusted to minimize flow rate variations. Investigators must ensure minimal flow rate changes at each injection site when increasing volume. Continue with the same infusion parameters at Weeks 9, 10, and 11.
- Weeks 12, 16, and 20: If the volume increase administered at Week 8 through Week 11 is tolerated, continue the step-down process until reaching the patient's maximum dose (in mL), maximum tolerated volume (maximum volume based on Investigator's decision of patient's tolerance), or 100 mL at 1 injection site (whichever is reached first) as described above. The same step-down procedure should be repeated as described at Week 16 and Week 20, if needed and based on the Investigator's decision of patient's tolerance.

Investigators should be aware that special considerations are required for volume increases in patients with 2 infusion sites receiving a total dose (volume) of more than 50 mL divided between 2 infusion sites. To ensure that volume increases do not exceed 25 mL/site, the infusions must be split between the 2 syringes, such that each infusion site will receive a different total volume. For example, if a patient is receiving a total dose of 60 mL divided equally between 2 infusion sites (eg, 30 mL/site), the first syringe could be increased to an infusion volume of 50 mL (an increase of 20 mL) and the second syringe would have an infusion volume of 10 mL. If this is tolerated, the next infusion volume increase could be 60 mL at 1 infusion site (an increase of 10 mL) and remain below the maximum allowed volume increase of 25 mL/site.

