If adverse drug reactions (ADRs) occur during an infusion, the patient may go back to the previous regimen that was tolerated if deemed necessary by the Investigator and/or patient; this would include reintroducing an injection site. This infusion regimen will continue until the next study visit at which the patient would again attempt to remove an injection site. If ADRs occur again, the patient may again go back to the previous stable regimen if deemed necessary until the next study visit. Following

unsuccessful attempts to increase volume, the Investigator and patient can cease or hold additional attempts and remain in the study; however, every effort to increase injection site volumes should be attempted.

Optional: When modifying the number of injection sites after previous unsuccessful attempts, the Investigator can make adjustments to lower the flow rate. This may include decreasing pump flow rate, revising the tubing, or changing needle gauge.

Note: Sites are encouraged to enroll patients into Cohort 1 who are already on a dosing regimen using at least 3 infusion sites to ensure that volume increases remain below limits listed in Table 6. Patients dosing with 1 infusion site cannot enter Cohort 1.

Cohort 2 (increased infusion rate - patients will receive CUTAQUIG weekly and increase infusion rates every 4 weeks): Patients will return to the clinic for the Treatment Period Baseline Visit, at which they will receive the same body-weight dependent (mg/kg) dose of CUTAQUIG but the infusion rate per site will be increased by up to a maximum allowed flow rate increase per infusion site of 25 mL/hr/site for patients ≥ 40 kg or 10 mL/hr/site for patients < 40 kg. Patients will receive this new flow rate for 4 weekly infusions (Treatment Period Baseline and Weeks 1, 2, and 3), and return to the clinic at Week 4 for their next infusion at an increased infusion rate. This cycle will continue, with maximum allowed flow rate increases per infusion site of up to 25 mL/hr/site for patients ≥ 40 kg or 10 mL/hr/site for patients < 40 kg every 4th infusion until reaching either 1) a maximum flow rate (100 mL/hr/site) or the maximum flow rate achievable by the pump, or 2) the maximum tolerated flow rate (maximum flow rate based on Investigator's decision of patient's tolerance) – whichever is reached first.

The following rate increases should be followed:

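### Cohort 1 step list and two-site split rule do not carry through the 10 mL/site limit for patients under 40 kg

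*Protocol*

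**What the plan says.** Protocol 3.3.2 (Cohort 1) sets the largest permitted rise per site by body weight: 25 mL/site at 40 kg or more, and "10 mL/site for patients < 40 kg every 4th infusion". The same pair of limits appears for Cohort 1 in the synopsis, the glossary, Table 2 footnote 6 and SAP 3.3. Table 6 in Protocol 5.5.3 repeats it, worded there as an approximate recommendation.

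A step list follows, introduced by "The following change in volume increments should be followed". It opens with "Baseline: Reduce the number of injection sites by 1", repeats the reduction at Week 4, and at Week 8 tells sites to "reduce the number of injection sites again by 1 (eg, patients using a 2 needle set will reduce to a 1 needle set"). The steps after Baseline depend on tolerance. None mentions weight or a volume limit.

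A two-site rule, given in 3.3.2 and in the synopsis, says that "special considerations are required for volume increases in patients with 2 infusion sites receiving a total dose (volume) of more than 50 mL". Its purpose and method are stated together: "To ensure that volume increases do not exceed 25 mL/site, the infusions must be split between the 2 syringes". The worked example takes 60 mL from 30/30 to 50/10 (+20 mL), then to 60 mL at one site (+10 mL).

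On entry, the only bar is "Patients dosing with 1 infusion site cannot enter Cohort 1". Sites are encouraged, but not required, to choose patients already using "at least 3 infusion sites to ensure that volume increases remain below limits listed in Table 6".

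**The concern.** The authors saw that removing a site can breach the per-site limit, and they wrote a rule to prevent it. That rule is built only on the limit for patients of 40 kg or more. For a lighter patient whose total is above 20 and up to 50 mL, the list calls for a 2-to-1 step that exceeds 10 mL/site, and no split instruction applies. Above 50 mL the split applies but protects the wrong limit for that patient.

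Patients from 2 years of age are eligible (Protocol 4.1), so the lower weight band can be populated. At stake is adherence to the plan's own safety limit in children: two sites reading the same subsection could give the same child different increases, one of them above the stated maximum.

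**Working it through.** **Inputs.** Limits of 25 and 10 mL/site (Protocol 3.3.2). Split trigger of 50 mL and the 60 mL example (3.3.2). Concentration of 165 mg/mL (1.1). The documents give no distribution of dose or weight; the weekly dose of 100 to 200 mg/kg used below is an assumption.

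**Formula.** With total volume V shared equally, going from k to k − 1 sites adds V/(k − 1) − V/k = V/(k(k − 1)) mL at each remaining site. A limit c is exceeded when V > c × k(k − 1). For the 2-to-1 step, the increase is V/2 and the threshold is 2c.

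**The plan's own figure.** With c = 25, the threshold is 2 × 25 = 50 mL, exactly the stated trigger. The example also reproduces: 50 − 30 = 20 and 60 − 50 = 10.

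**The same rule below 40 kg.** With c = 10, the threshold is 2 × 10 = 20 mL.
- V = 30 mL: 30/2 = +15 mL, 1.5 times the limit.
- V = 40 mL: 40/2 = +20 mL, 2.0 times the limit.

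**Which step is affected.** The 3-to-2 step adds V/6 and reaches 10 mL only at V = 60 mL (30 mL adds 5.0; 40 mL adds 6.7). The 4-to-3 step adds V/12 and reaches 10 mL only at 120 mL. The gap is therefore the last step. A patient entering on two sites meets it at Baseline, and one entering on three meets it at Week 4, so the encouragement to enrol patients with at least three sites postpones the problem without removing it.

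**Plausible size.** V = dose × weight/165, and the increase is V/2. The dose at which V reaches 20 mL is 20 × 165/weight.

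| Weight | V at 100 to 200 mg/kg | 2-to-1 increase | Dose giving 20 mL |
|---|---|---|---|
| 20 kg | 12.1 to 24.2 mL | 6.1 to 12.1 mL | 165 mg/kg |
| 25 kg | 15.2 to 30.3 mL | 7.6 to 15.2 mL | 132 mg/kg |
| 30 kg | 18.2 to 36.4 mL | 9.1 to 18.2 mL | 110 mg/kg |
| 39 kg | 23.6 to 47.3 mL | 11.8 to 23.6 mL | 85 mg/kg |

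At the low end of the assumed range, the step stays within 10 mL up to 30 kg. A 50 mL total at 39 kg needs 50 × 165/39 = 211.5 mg/kg/week, so totals of 50 mL or more fall outside the range.

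**The case against.** The strongest reply is that the limit already governs. It is stated in several places, including the paragraph directly above the step list, and site reduction is presented as one means of achieving a capped increase. A listed means does not override a stated maximum. The enrolment note also points to Table 6, which gives both weight bands. This stands: a reader might infer that the protocol orders children past 10 mL/site, and the documents do not support that.

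The half-volume figure assumes two equal sites. An unequal split avoids the breach, and a site could borrow that device for a child. That is correct, but the protocol gives the instruction only above 50 mL and only for the 25 mL limit.

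The approximate wording in Table 6 may absorb a small excess, such as 12.1 mL at 20 kg. It is harder to stretch to twice the limit.

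A reader might also infer that uneven steps undermine the Cohort 1 assessment. The objective concerns tolerability at increased volumes per site, not step size. Increases are up to a maximum, with Investigator judgement and reversal allowed, so step size varies by design. The comparability argument therefore falls away.

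Finally, increases require two tolerated prior administrations (5.5.3), a site can be reintroduced after a reaction, and the total dose is unchanged. These are real protections, but they settle whether to step up and what to do afterwards. They do not set how far to step.

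**Conclusion.** The inconsistency is real. For patients under 40 kg, the split should start above 20 mL total, and the protocol starts it above 50 mL. Followed literally, the step list gives +15 mL at 30 mL and +20 mL at 40 mL against a limit of 10 mL. Under the assumed 100 to 200 mg/kg/week, the increase is at most about 12 mL at 20 kg, 18 mL at 30 kg and 24 mL at 39 kg. These figures rest on an equal split and on a dose range that is not in the documents.

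The reach is limited. The number of patients under 40 kg among the at least 15 in Cohort 1 is not given and may be zero. The documents do not show that the larger step worsens tolerability. Cohort 1 is descriptive and the Cohort 3 test is untouched, so no analysis changes. The 50 mL case, at 2.5 times the limit, is arithmetically possible but should not be presented as typical.

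**What to change.** In Protocol 3.3.2 and the synopsis:
- State that the weight-specific maximum overrides every site-reduction step.
- Apply the two-site split above 20 mL total for patients under 40 kg (at most 10 mL/site per step), and above 50 mL total for patients of 40 kg or more (at most 25 mL/site per step).
- Add an example for under 40 kg: 30 mL as 15/15, then 25/5 (+10), then 30 mL at one site (+5).

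The pointer in 5.5.3, which names only the 50 mL threshold, should follow. As minor tidying, add the 10 mL/hr/site limit to the Cohort 2 Baseline step; the paragraph above that list already states it.

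The cost is a wording amendment, submitted as Protocol 10.4 requires. Some patients under 40 kg would reach one site later. Steps needed from n sites become (n − 2) + (V/2)/10 rounded up, against n − 1 as written. At 30 or 40 mL that is one extra 4-week step (from four sites, Week 12 instead of Week 8); above 40 and up to 50 mL it is two. A few patients may need the otherwise optional Week 16 or 20 visit: from five sites at 30 or 40 mL, one site is reached at Week 16 instead of Week 12. No extra patients or analyses are needed.

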- Baseline: Increase infusion rates up to 25 mL/hr/site. This can be accomplished by increasing the tubing set, needle gauge, and adjusting pump rates (if applicable). Continue with the same infusion parameters at Weeks 1, 2, and 3.
- Week 4: If the infusion rate increase administered at Baseline through Week 3 is tolerated, increase infusion rates again by up to 25 mL/hr/site for patients ≥ 40 kg or 10 mL/hr/site for patients < 40 kg. This can be accomplished by increasing the tubing set, increasing needle gauge, or adjusting pump rates (if applicable). Continue with the same infusion parameters at Weeks 5, 6, and 7.
- Week 8: If the infusion rate increase administered at Week 4 through Week 7 was tolerated, increase infusion rates again by up to 25 mL/hr/site for patients ≥ 40 kg or 10 mL/hr/site for patients < 40 kg. This can be accomplished by revising the tubing, increasing needle gauge, or adjusting pump rates (where applicable). Continue with the same infusion parameters at Weeks 9, 10, and 11.
- Weeks 12, 16 and 20: If necessary and if the infusion rate increase administered at Week 8 through Week 11 was tolerated, the patient should continue the rate increase process as described above.

Note: Clinical sites are encouraged to enroll patients that are either currently infusing with 24-gauge needle sets or willing to switch to 24-gauge needle sets. Patients using 27-gauge needles will not be able to achieve adequate infusion rates for this cohort as the needle gauge will not allow for this.

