5.5.3 Infusion Flow Rates

- The maximum recommended flow rate is 100 mL/hr/infusion site.
- The maximum infusion rate for all sites combined is 240 mL/hr.
- Infusion volumes and flow rates may only be increased if the previous 2 administrations were tolerated by the patient, and deemed appropriate by the Investigator.
- Infusion volume and flow rate should be increased gradually as tolerated to prevent infusion site reactions. See the parameters listed in Table 6.

Table 6: Infusion Volume and Flow Rate by Patient Weight

	Recommended Increase for Patients <40 kg	Recommended Increase for Patients ≥ 40 kg
Infusion Volume mL/site per infusion cycle	Approximately ≤ 10 mL/site	Approximately ≤ 25 mL/site
Infusion Flow Rate mL/hour/site per infusion cycle	≤ 10 mL/hour/site	≤ 25 mL/hour/site

Note: To account for non-precision flow rates of pumps, actual flow rate increases will be dependent on tubing size, number of infusion sites, and needle gauge. Minor deviations in flow rates (<2 mL/site) would not be considered protocol deviations.

Instructions for performing volume increases in Cohort 1 patients who are using 2 infusions sites with a total volume of ≥ 50 mL are provided in Section 3.3.2.

If AEs occur during an infusion, the flow rate and volume may be reduced if deemed necessary by the Investigator and/or patient to the previous flow rate and volume at which no AE occurred. If appropriate, the infusion may be interrupted until symptoms subside. The infusion may then be resumed at a flow rate or volume tolerated by the patient.

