Cohort 2 (increased infusion rate - patients will receive CUTAQUIG weekly and increase infusion rates every 4 weeks): Patients will return to the clinic for the Treatment Period Baseline Visit, at which they will receive the same body-weight dependent (mg/kg) dose of CUTAQUIG but the infusion rate per site will be increased by up to 25 mL/hr/site for patients ≥ 40 kg or 10 mL/hr/site for patients < 40 kg. Patients will receive this new flow rate for 4 weekly infusions (Treatment Period Baseline and Weeks 1, 2, and 3), and return to the clinic at Week 4 for their next infusion at an increased infusion rate. This cycle will continue, with flow rates increased up to 25 mL/hr/site for patients ≥ 40 kg or 10 mL/hr/site for patients < 40 kg every 4th infusion until reaching either a maximum flow rate (100 mL/hr/site) or maximum tolerated flow rate (maximum flow rate based on Investigator's decision of patient's tolerance) is reached.

Cohort 3 (every other week dosing - patients will receive CUTAQUIG every other week at the equivalent of twice their weekly body-weight dependent [mg/kg] dose): Patients will return to the clinic for the Treatment Period Baseline visit to receive their first double mg/kg weekly dose and begin an every other week dosing schedule. Infusion volumes increases per site must not exceed 25 mL at the Treatment Period Baseline visit. If a patient's doubling of their weekly dose requires dosing with a volume of more than 25 mL per injection site, then they will be required to increase the number of infusion sites to remain below the maximum of 25 mL/site volume increase. If this occurs, after 2 infusions the patient may remove one of the newly introduced injection sites as long as the 25 mL/site increase limit is not exceeded.

Approximately 65 patients between the ages of ≥ 2 years and ≤ 75 years are planned for enrollment for the study into one of the following three cohorts:

- At least 15 patients in Cohort 1

- At least 15 patients in Cohort 2
- At least 35 patients in Cohort 3

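### The Cohort 2 Baseline step in Protocol 3.3.2 gives 25 mL/hr/site with no weight band, contradicting the separate under-40 kg figure stated everywhere else for Cohort 2

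*Protocol*

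**What the plan says.** Protocol 3.3.2 describes Cohort 2 in a lead paragraph followed by a visit-by-visit list. For the Treatment Period Baseline Visit, the lead paragraph sets a "maximum allowed flow rate increase per infusion site of 25 mL/hr/site for patients ≥ 40 kg or 10 mL/hr/site for patients < 40 kg".

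The list is introduced by "The following rate increases should be followed". Its first item is "Baseline: Increase infusion rates up to 25 mL/hr/site", with no weight qualifier. The Week 4 item returns to two bands: "increase infusion rates again by up to 25 mL/hr/site for patients ≥ 40 kg or 10 mL/hr/site for patients < 40 kg". Week 8 has the same bands, and Weeks 12, 16 and 20 refer back to the process above.

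Protocol 5.5.3, Table 6, also has two weight columns, one of them headed "Recommended Increase for Patients <40 kg". The flow-rate entries are at most 10 and at most 25 mL/hour/site per infusion cycle.

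SAP 3.3 gives both bands for Cohort 2. For Cohort 3, which concerns volume and not rate, it says only: "Infusion volumes increases per site must not exceed 25 mL at the Treatment Period Baseline visit".

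**The concern.** The Baseline step is the first escalation in the cohort that exists to test higher rates. The list is presented as the sequence to follow, so a site may use it as a checklist. The rate set at Baseline carries through Weeks 1, 2 and 3, and infusions between site visits are given at home (Protocol 3.3.2 and 6.1.3). A patient under 40 kg could be stepped up by an amount that complies with the list item but breaches the limit in the paragraph above it.

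A second ambiguity affects patients of any weight. The Baseline item says *up to*, where Weeks 4 and 8 say *by up to*. Taken alone, it leaves open whether 25 mL/hr/site is the size of the step or the rate to be reached.

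There is also a data-handling consequence. Adverse events by infusion speed are among the co-primary variables (Protocol 3.1.1), and patients not treated according to their cohort's regimen leave the per-protocol set (Protocol 9.2.1, SAP 6). Whether a given step is a deviation depends on which text is applied.

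**Working it through.** **1. The Cohort 2 passages side by side** (mL/hr/site)

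| Place | Does it cover Baseline? | ≥ 40 kg | < 40 kg |
|---|---|---|---|
| Protocol 3.3.2, Baseline step | yes | 25, no band | 25, no band |
| Protocol 3.3.2, lead paragraph | yes, by name | 25 | 10 |
| Protocol 3.3.2, Week 4 and Week 8 steps | no | 25 | 10 |
| Study Outline, Cohort 2 | yes, by name | 25 | 10 |
| Glossary, Cohort 2 | yes, by name | 25 | 10 |
| Table 3, footnote 6 | yes, through the infusion row it annotates | 25 | 10 |
| Table 6 (5.5.3) | per infusion cycle, no visit named | 25 | 10 |
| SAP 3.3, Cohort 2 | yes, by name | 25 | 10 |

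Only the Baseline step differs.

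**2. Can it apply to anyone?** Protocol 4.1 and 4.1.1 admit patients aged 2 to 75 years. No minimum weight is stated, and neither the entry criteria nor the Cohort 2 text bars patients under 40 kg from that cohort. The documents do not say how many are expected.

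**3. Size, increment reading.** Ratio = increase allowed by the step ÷ increase stated elsewhere for < 40 kg = 25 / 10 = 2.5.

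**4. Size, target-rate reading.** If 25 is the rate to be reached from a prior rate r0, the increase is 25 − r0 and the ratio is (25 − r0) / 10. The documents give no prior rates, so the r0 values are assumptions:

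- r0 = 5: 20 / 10 = 2.0
- r0 = 10: 15 / 10 = 1.5
- r0 = 15: 10 / 10 = 1.0, no excess
- r0 above 15: below 1.0, no excess

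So 2.5 is the maximum under either reading.

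**5. The wording at 40 kg or more.** With an assumed prior rate of 20 mL/hr/site, the increment reading allows 20 + 25 = 45 and the target reading allows 25. At a prior rate of 25 or more, the target reading allows no increase at all.

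**6. Deviation status.** Suppose a patient under 40 kg is stepped up by 20 mL/hr/site. On the increment reading this is within the list item. It is 20 − 10 = 10 above the figure stated elsewhere, well beyond the tolerance of less than 2 mL/site in the note under Table 6.

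**7. SAP Cohort 3.** The protocol's Cohort 3 text (Study Outline, Table 4 footnote 5, glossary, 3.3.2) limits the volume increase to 25 mL/site at 40 kg or more and 10 mL/site below. SAP 3.3 gives 25 mL only, although it keeps both bands for Cohorts 1 and 2.

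**The case against.** The strongest reply is that the protocol already answers the question for this visit. The banded limit stands directly above the list, names the Baseline Visit and is called a maximum. A site that reads the whole section will see it, so the error bites only when the list item is used alone. That stands and limits the practical risk, but it does not remove the contradiction, because the same section says that the list is to be followed.

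The wording ambiguity is also weaker than it looks. The list is introduced as rate increases, the Week 4 item refers back to the Baseline increase, and the Study Outline uses *up to* together with a maximum increase. The context favours the increment reading, although the item itself does not say so.

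A reader might go further than the documents allow in five ways:

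- **That the omission is deliberate**, because later steps repeat both bands. Nothing supports this, and four passages that name Baseline carry both bands.
- **That 2.5-fold is the expected excess.** It needs the full step, a patient under 40 kg and the increment reading (or a prior rate near zero). It is an upper bound.
- **That a paediatric limit or an absolute rate limit is breached.** The band depends on weight, not age, and concerns the size of a step. The 100 mL/hr/site maximum is a separate matter.
- **That the confirmatory result is threatened.** The only confirmatory test is on IgG troughs in Cohort 3. Safety endpoints use the Safety Analysis Set under the original cohort assignment. A change in Cohort 2 per-protocol membership would touch only repeated descriptive analyses.
- **That the SAP's Cohort 3 omission corroborates a Cohort 2 dosing risk.** It concerns volume in another cohort, in a document that does not direct dosing and refers readers to the protocol for study conduct.

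**Conclusion.** The contradiction is real and confined to one list item. Read literally, the Cohort 2 Baseline step permits an increase in patients under 40 kg that the lead paragraph and the other Cohort 2 passages do not. The excess is at most 2.5 times the figure stated elsewhere; on a target-rate reading it is smaller and vanishes at an assumed prior rate of 15 mL/hr/site or more. How many patients could be affected cannot be judged, because the documents give neither prior rates nor the number under 40 kg in Cohort 2.

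This is an internal inconsistency with a safety bearing, not a flaw in the design or the primary analysis. Which limit is right is not judged here. The SAP Cohort 3 omission is a separate, minor consistency point.

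**What to change.** Reconcile the Cohort 2 Baseline step in Protocol 3.3.2 with the lead paragraph, the Week 4 and Week 8 steps, the Study Outline, the glossary, Table 3 footnote 6, Table 6 and SAP 3.3. The reconciled text should settle two things: whether weight bands apply at this step, and whether the figure is an increment or a target rate. The sponsor must confirm the intended limit. It would help to settle at the same time whether the Table 6 values are recommendations, as its column headings say, or maxima, as 3.3.2 says.

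Separately, reconcile the Cohort 3 volume text in SAP 3.3 with the protocol's Cohort 3 text.

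If Cohort 2 dosing has already been completed, the sponsor should record which text governed deviation and per-protocol decisions. The cost is a wording change in each document, with no effect on sample size, visits or analyses.
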